## Duration of treatment

Following the screening period’s two confirmatory pre-dialysis  $K^+$  measurements and after meeting study eligibility criteria, patients will be referred to the electrophysiology cardiologist of choice by the site principal investigator where a sub-cutaneous (SQ) continuous cardiac loop recorder will be placed in the left anterior chest wall. Patients will be allowed to accommodate to the loop recorder for 2-weeks before they are randomized (1:1 ratio) to one of two treatment sequences (Sequence A or B, as described above), and start study treatment with 2.0  $K^+$ /2.5 $Ca^{++}$  dialysate bath without potassium binder supplementation or 3.0  $K^+$ /2.5  $Ca^{++}$  dialysate bath with Lokelma supplementation (taken on off-dialysis days). There will be a **2-week** cardiac monitoring blanking period where patients will be allowed to accommodate to the higher  $K^+$  dialysate and the use of Lokelma. Any data recorded by the insertable loop recorder (ILR, LINQ device) during this time period will not be used for any endpoint analysis. During the next **8-week** treatment period (Phase I of the study), patients will undergo continuous cardiac monitoring by the ILR. At the end of Phase I, data will be downloaded from the ILR and a new **2-week** blanking period will begin where patients will “cross-over” to the alternative dialysate bath and will be allowed to equilibrate to the new dialysate. Patients dialyzed for 8 weeks using a 2.0  $K^+$ /2.5 $Ca^{++}$  bath (without potassium binder supplementation) during Phase I will be switched to the 3.0  $K^+$ /2.5  $Ca^{++}$  bath with Lokelma supplementation, and *vice versa*. During the subsequent **8-week** treatment period (Phase II of the study), patients will undergo continuous cardiac monitoring by the ILR. At the conclusion of Phase II, a new cardiac monitoring blanking period will begin and blood sampling will be stopped. The ILR will be removed by the affiliated electrophysiology cardiologist. This process may take an additional 2 weeks. Therefore, for each patient, the planned total study treatment duration will be **20 weeks**, and the total study participation will be approximately **25 weeks**.

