[2] During the treatment period (both 2-week accommodation periods and 8-week Treatment phases), a second Piccolo POCT is performed promptly before dialysis end and within 30 minutes prior to rinse back on Mondays or Tuesdays after each long dialysis weekend (i.e., weekly), to measure K+, Ca++ and PO4.

[3] Applies only to the first twenty-five (25) patients randomized receiving standard treatment (hemodialysis using 2.0K+/2.5 Ca++ dialysate bath, without Lokelma supplementation) during Treatment Phase-1. Performed weekly, on Mondays or Tuesdays after each long dialysis weekend, promptly before dialysis end and within 30 minutes prior to rinse back.

[4] Performed weekly, on Mondays or Tuesdays after each long dialysis weekend, promptly before dialysis end and within 30 minutes prior to rinse back. Mg++ levels will be determined by the local laboratory at each site.

[5] Performed (if possible) upon symptomatic muscle cramping, promptly before dialysis end and within 30 minutes prior to rinse back. Mg++ levels will be determined by the local laboratory at each site.

[6] Baseline/Randomization is conducted on Week 1 of the new Dialysate Accommodation Period 1. Crossover occurs on the same day as Week 11 of the new Dialysate Accommodate Period 2. Neither Baseline/Randomization nor Crossover will be considered a separate visit.

[7] If ILR insertion is performed more than 30 days after the last K+ Piccolo POCT determination, please contact the sponsor who will determine if an additional K+ Piccolo POCT determination will be required prior to the baseline visit. These will be handled on a case-by-case basis.

[8] Adverse events will be collected from the time of first dose of Lokelmaâ, throughout the treatment and post-treatment follow-up period, up to the last study visit.

[9] SAEs will be reported from the time the patient signed the Informed Consent Form.

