### 4.2.1 Blood Draws (Weeks 3 to 10 and Weeks 13 to 20)

During both 8-week treatment phases, the first twenty-five (25) patients randomized receiving standard treatment (hemodialysis using 2.0K+/2.5 Ca++ dialysate bath, without Lokelma supplementation) will undergo blood collection for select chemistry tests and determination of protein-bound uremic toxins (PBUTs).

Blood will be drawn as follows:

- 1) A 4.0 ml Green Top tube will be drawn from the dialysis line after placement of the dialysis needles and BEFORE the initiation of dialysis. The Green Top tube will be in & out inverted 3 times and then used for Piccolo POCT measurements of K+, Ca++ and PO4, as described in [Section 8](#). This will be repeated promptly before the anticipated termination of the dialysis session and within 30 minutes prior to rinse back.
- 2) Treatment Phase-1 only: Two 4.0 ml Purple Top tubes will be drawn from the first twenty-five (25) patients receiving standard treatment (hemodialysis using 2.0K+/2.5 Ca++ dialysate bath, without Lokelma supplementation) by the same method (as described above) and centrifuged. Each tube of plasma (approximately 1ml after processing) will be transferred to a 1.0 ml O-Ring sealed cryovials (two cryovials pre-dialysis and two cryovials promptly before the anticipated termination of the dialysis session and within 30 minutes prior to rinse back) and frozen at -80°C until analyzed for measurement of pre- and post-dialysis concentrations of the following PBUTs: p-Cresol sulfate (PCS), indoxyl sulfate, and asymmetric dimethylarginine (ADMA). Measurement of pre- and post-dialysis levels will be conducted by an outside vendor using gas chromatography-mass spectrometry (GC-MS) ([Tsikas et al. 2003](#)).
- 3) 5) A 5.0 ml Yellow Top SST tube will be drawn from the dialysis line promptly before the anticipated termination of the dialysis session (and within 30 minutes prior to rinse back) will be sent to the local laboratory for routine measurement of Mg++ levels.
- 4) A 2nd 4.0 ml Green Top tube will be drawn from the dialysis line promptly before the anticipated termination of the dialysis session (and within 30 minutes prior to rinse back) for Piccolo POCT measurement of post-dialysis electrolytes (K+, Ca++ and PO4), as described in [Section 8](#).

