**Figure 10 – Patient Assistant**

### **4.2.3 Cross-Over (Week 11)**

At the end of the first treatment phase (Weeks 3 to 10) of the study, all blood draws will be stopped for 2 weeks. Cardiac loop recording devices will not be interrogated during this 2-week accommodation period, and the data recorded during that time will not be used for analysis. Patients who completed treatment with experimental 3.0 K+/2.5 Ca++ dialysate with Lokelma supplementation (on off-dialysis days) during Treatment Phase-1 will be crossed over to standard 2.0 K+/2.5 Ca++ dialysate with no Lokelma supplementation for Treatment Phase-2. Patients who completed treatment with standard 2.0 K+/2.5 Ca++ dialysate with no Lokelma supplementation during Treatment Phase-1 will cross-over to experimental 3.0 K+/2.5 Ca++ dialysate with Lokelma supplementation (on off-dialysis days) for Treatment Phase-2.

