#### **8.4.7 Safety Endpoint #2: Incidence of Dialysis-related Hypokalemia, Hypomagnesemia, Hypophosphatemia, or Low Calcium**

This endpoint is defined as the number of events promptly prior to the termination of dialysis where a Piccolo POCT measurement of  $K^+$  is  $< 2.0$  mEq/L OR  $Ca^{++}$  is  $< 7.0$  mEq/L, OR  $Mg^{++}$  is  $< 2.0$  mg/dl OR a  $PO_4$  level is  $< 3.0$  mEq/L.

All episodes where a specific electrolyte falls below the above listed threshold will be considered an “event” for that electrolyte. The total number of “events” will be recorded during the 8-week Treatment Phase-1 and the 8-week Treatment Phase-2 cross-over periods. Each electrolyte will be its own “safety” objective independently.

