#### **8.5.6 Safety Analyses**

Lokelma-induced hypokalemia will be evaluated based on the total number of hypokalemic events defined as PiccoloPOCT or laboratory-measured K+ of < 3.5 mEq/L.

The incidence of dialysis-related hypokalemia, hypomagnesemia, hypophosphatemia, and low calcium will be evaluated based on the number of events promptly prior to the termination of dialysis where a PiccoloPOCT measurement of K+ is < 2.0 mEq/L OR Ca++ is < 7.0 mEq/L, OR Mg++ is < 2.0 mg/dl, OR a PO4 level is < 3.0 mEq/L. All episodes where a specific electrolyte falls below the above listed threshold will be considered an “event” for that electrolyte. The total number of “events” will be recorded during the 8-week Treatment Phase-1 and the 8-week Treatment Phase-2 cross-over periods and compared between the treatments.

Safety will also be assessed in terms of the frequency of AEs, SAEs, and withdrawals due to AEs, with focus on treatment-related events. Appropriate summaries of these data will be presented by treatment group and/or study period.

Adverse events will be coded using the Medical Dictionary for Regulatory Activities (MedDRA) system organ class (SOC) and preferred term (PT). A treatment-emergent AE

(TEAE) is defined as an AE with the start date on or after the first dose date and up to (and including) 14 days after the last dose date in each of study periods when patients received 3K Bath with Lokelma. However, when patients received 2K Bath without Lokelma, A treatment-emergent AE (TEAE) is defined as an AE with the start date on or after the first visit date and up to (and including) 14 days after the last visit date in each of study periods. Only TEAEs will be included in table summaries.

The number and percentage of participants experiencing AEs, SAEs, AEs that led to withdrawal, AEs that led to death, and the number of such events, will be summarised by SOC, PT, and treatment group and study period. The number and percentage of participants experiencing AEs will further be summarised by intensity and will be presented with the number of events at each level of intensity.

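### Safety endpoint #2 compares raw totals of low-electrolyte events between the two baths with no denominator, although the number of samples can differ by bath

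*Protocol*

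**What the plan says.** **Endpoint.** Sections 2.3, 8.4.7 and 8.5.6 define safety endpoint #2 as a number of events, taken just before dialysis ends, for K+, Ca++, Mg++ and PO4, each judged on its own. Repeats count: "All episodes where a specific electrolyte falls below the above listed threshold will be considered an" event. In Section 8.4.7 the total "will be recorded during the 8-week Treatment Phase-1 and the 8-week Treatment Phase-2 cross-over periods", and Section 8.5.6 adds the comparison: the total "will be recorded during the 8-week Treatment Phase-1 and the 8-week Treatment Phase-2 cross-over periods and compared between the treatments". No rate, number of samples or exposure time is mentioned. The primary analysis (Section 8.5.2) does carry log period duration as an offset.

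**Sampling.** Table 1 marks end-of-dialysis K+, Ca++, PO4 and Mg++ in both accommodation periods and both treatment phases. Footnote [2] is explicit for the first three: "During the treatment period (both 2-week accommodation periods and 8-week Treatment phases), a second Piccolo POCT is performed promptly before dialysis end". Footnote [4] covers Mg++: "Performed weekly, on Mondays or Tuesdays after each long dialysis weekend, promptly before dialysis end and within 30 minutes prior to rinse back". Section 4.2.3, however, says that at cross-over "all blood draws will be stopped for 2 weeks", and the heading of Section 4.2.1 lists only Weeks 3 to 10 and 13 to 20.

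**Exclusion of accommodation data.** The synopsis, under Duration of treatment, excludes loop-recorder data: "Any data recorded by the insertable loop recorder (ILR, LINQ device) during this time period will not be used for any endpoint analysis". No equivalent rule is written for laboratory safety values.

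**The concern.** A total of repeated events depends on two things: the risk at each sample and how many samples were taken. If one treatment has fewer samples, its total is lower even when the risk is the same. The protocol contains a mechanism that can cause this. A patient who misses the K+ target after the top Lokelma dose step is withdrawn from the study (Section 7.2.1), and no such rule applies on the 2.0 K+ bath. A reader of the safety table could then take a shortfall in samples on 3.0 K+ for a lower rate of low electrolytes.

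A second, smaller question concerns the counting window. The accommodation weeks include the start of Lokelma and the first sessions on a new bath. Section 8.5.6 counts treatment-emergent adverse events from the first dose or first visit of each period, but endpoint #2 starts at Week 3 or Week 13. Whether any samples are affected depends on a sampling schedule on which the protocol disagrees with itself.

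**Working it through.** The protocol states no sample count or event rate for this endpoint. Its one figure to reproduce is the planned treatment duration: 2 + 8 + 2 + 8 = 20 weeks, as stated.

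**Inputs.** 88 patients, 44 per sequence (Section 8.2); one end-of-dialysis sample per week (Table 1); 8 counted weeks per treatment (Section 8.4.7). Sequence labels follow Section 3.5, where A is 2.0 K+ first; Table 4 reverses them. Assumed: a fraction f of 3.0 K+ phases stops after 2 of 8 counted samples, and risk per sample is equal on both baths. The protocol gives only 10% overall non-completion, so f is taken as 10% and 20%.

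**Effect on raw totals.**

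- 3.0 K+ samples, relative to full attendance: 1 − f × 6/8. This gives 0.925 at 10% and 0.85 at 20%.
- If no 2.0 K+ samples are lost, these are the ratios of the totals: 7.5% and 15% lower on 3.0 K+.
- If withdrawn Sequence B patients also lose their later 2.0 K+ phase, the 2.0 K+ samples are 1 − f/2, which is 0.95 and 0.90. The ratios become 0.925/0.95 = 0.974 and 0.85/0.90 = 0.944: 2.6% and 5.6% lower.
- With stopping after 1 of 8 samples, the same two cases give 0.961 to 0.913 at 10% and 0.917 to 0.825 at 20%.

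With events per sample obtained, the ratio at equal risk is 1.00 whatever the sample numbers.

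**Share of scheduled samples outside the counting window, per patient.**

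| Governing text | Samples taken | Uncounted | Share |
|---|---|---|---|
| Table 1, footnotes [2] and [4] | 20 | 4 | 20% |
| Section 4.2.3 (none in Weeks 11 and 12) | 18 | 2 | 11% |
| Heading of Section 4.2.1 | 16 | 0 | 0% |

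Under Table 1 this is 88 × 4 = 352 of 88 × 20 = 1,760 samples.

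**The case against.** **The denominator may come in the SAP.** Section 8.5.6 says that safety is in general reported descriptively and that full details follow in the SAP. A per-sample rate could appear there. This stands in part. But the protocol itself fixes the measure as a total and says that totals are compared, so the remedy belongs in the protocol text.

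**The 8-week window is not arbitrary.** Footnotes in Section 2.3 define both treatments as 8 weeks, and the accommodation weeks exist so that patients can adapt. This stands: leaving those weeks out of the main count is defensible. It does not explain why they have no event summary of their own.

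**Accommodation-week values are not lost.** A reader might infer that the plan throws away a fifth of the safety samples. It does not. The values reach the listings and the shift tables to the worst value in each period (Section 8.5.6), and endpoint #1 (Section 8.4.6) has no 8-week limit for K+. The 20% itself holds only if Table 1 governs. Nor do all these weeks follow a bath change: a Sequence A patient already on 2.0 K+ has none at Week 1.

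**The bath with more early exits need not look safer.** A Sequence B patient withdrawn in this way loses 6 of 8 samples on 3.0 K+ but all 8 on 2.0 K+, so the bias reverses within that sequence. The net deficit on 3.0 K+ comes from Sequence A. Section 3.9 also keeps patients who only stop the product in scheduled visits, so their samples need not be missing. For these reasons 7.5% and 15% are upper ends under the 2-of-8 assumption and not expected values.

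**Conclusion.** The comparison of raw totals is a real but modest weakness. At equal risk per sample, the 3.0 K+ total would be about 3% to 7.5% lower if 10% of 3.0 K+ phases stop after 2 of 8 samples, and about 6% to 15% lower if 20% do. The lower ends apply when withdrawn Sequence B patients also lose their 2.0 K+ phase. The stopping fractions and the timing are assumptions. So is equal risk for withdrawn patients: those withdrawn for high K+ may have fewer low-K+ events, which would make the deficit for K+ smaller.

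The window question is secondary. The documents do not support saying that 20% of the safety data are discarded. They support saying that the schedule contradicts itself, that between 0% and 20% of samples fall outside the window depending on which text governs, and that accommodation-week events have no summary for this endpoint.

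**What to change.** 1. In Sections 8.4.7 and 8.5.6, replace the comparison of totals with events per end-of-dialysis sample obtained, for each electrolyte and treatment. Give the number of samples beside each rate. If a model is wanted, the count model of the primary analysis with log number of samples as offset and robust intervals would serve. A rate removes the dependence on sample numbers but not any selection in who is withdrawn, so withdrawals by treatment and sequence should be shown beside it.
2. Reconcile Table 1 with its footnotes [2] and [4], the heading of Section 4.2.1, and Section 4.2.3 on whether samples are drawn in Weeks 1 and 2 and Weeks 11 and 12. Reconcile Sections 3.9 and 7.2.1 on whether patients who stop Lokelma for high K+ stay in follow-up, since this decides how many samples go missing.
3. If accommodation-week samples are taken, show their events in a separate row by treatment, in line with the adverse events counted from the start of each period. Keep the 8-week count as the main row.

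The cost is wording and programming. If Table 1 governs, no samples are added; if the heading of Section 4.2.1 governs, the separate row falls away. The first accommodation sample follows very little time on the new bath, which a separate row makes visible.

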
To evaluate whether the use of Lokelma during periods when patients are receiving a 3.0 K+/2.5 Ca++ bath is associated with hypokalemic events defined as K+ <3.5 mEq/L.
	
 
➤ Total number of hypokalemic events defined as Piccolo Point of Care Testing (POCT) or laboratory-measured K+ of < 3.5 mEq/L.
 

Safety Objective #2: Incidence of Dialysis-related Hypokalemia, Hypomagnesemia, Hypophosphatemia, or Low Calcium	Safety Outcome Measure:

To determine the levels of K+, Mg++, calcium and PO4 during dialysis (measured promptly prior to the termination of dialysis) during experimental treatment [2] compared to standard treatment [3].
 
Note: Each electrolyte is its own "safety" objective independently.
	
➤ Number of events (measured promptly prior to the termination of dialysis) where a Piccolo POCT measurement of K+ is < 3.5 mEq/L OR Ca++ is < 7.0 mEq/L, OR Mg++ is < 2.0 mg/dl OR a PO4 level is <3.0 mEq/L.
 
All episodes where a specific electrolyte falls below the above listed threshold will be considered an "event" for that electrolyte. The total number of "events" will be recorded during the 8-week Treatment Phase-1 and the 8-week Treatment Phase-2 cross-over periods.

Safety Objective #3: Adverse Experiences
	
Safety Outcome Measure:

To evaluate the safety and tolerability of the experimental treatment [2] compared to standard treatment [3] based on the frequency of reported adverse experiences.
	
➤ Frequencies of AEs, SAEs, and withdrawals due to AEs, with focus on treatment-related events.

Exploratory Objectives:
	
Exploratory Outcome Measures:

1) To evaluate the relationship between protein-bound uremic toxins (PBUTs) and atrial fibrillation rates. PBUTs such as indoxyl sulfate (IS) and p-Cresol sulfate (PCS) can induce atrial fibrillation (Aoki et al. 2015; Tang et al. 2015).
	
➤ Correlation between PBUTs (IS, PCS, and ADMA) and the frequency of atrial fibrillation events.

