## 2.3 Safety Objectives

Safety Objective #1: Lokelma-Induced Hypokalemia	Safety Outcome Measure:
To evaluate whether the use of oral sodium zirconium cyclosilicate (Lokelma ® ) during periods when patients are receiving a 3.0 K + /2.5 Ca ++ dialysate bath is associated with hypokalemic events defined as K + <3.5 mEq/L.	➤ Total number of hypokalemic events defined as Piccolo POCT or laboratory-measured K + of < 3.5 mEq/L.
Safety Objective #2: Incidence of Dialysis-related Hypokalemia, Hypomagnesemia, Hypophosphatemia, or Low Calcium	Safety Outcome Measure:
To determine the levels of K + , Mg ++ , calcium and PO 4 during dialysis (measured promptly prior to the termination of dialysis) during experimental treatment [2] compared to standard treatment [3]. Note: Each electrolyte is its own "safety" objective independently.	➤ Number of events (measured promptly prior to the termination of dialysis) where a Piccolo POCT measurement of K + is < 3.5 mEq/L OR Ca ++ is < 7.0 mEq/L, OR Mg ++ is < 2.0 mg/dl, OR a PO 4 level is <3.0 mEq/L. All episodes where a specific electrolyte falls below the above listed threshold will be considered an "event" for that electrolyte. The total number of "events" will be recorded during the 8-week Treatment Phase-1 and the 8-week Treatment Phase-2 cross-over periods.
Safety Objective #3: Adverse Experiences	Safety Outcome Measure:
To evaluate the safety and tolerability of the experimental treatment [2] compared to standard treatment [3] based on the frequency of reported adverse experiences.	➤ Frequencies of AEs, SAEs, and withdrawals due to AEs, with focus on treatment-related events.

Abbreviations: AE=adverse event; CSCA=clinically significant cardiac arrhythmia; SAE=serious adverse event

[2] Experimental treatment (8 weeks): hemodialysis using 3.0K+/2.5 Ca++ dialysate bath, with sodium zirconium cyclosilicate (Lokelma®) supplementation on off-treatment days

[3] Standard treatment (8 weeks): hemodialysis using 2.0K+/2.5 Ca++ dialysate bath, without sodium zirconium cyclosilicate (Lokelma®) supplementation

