Additionally, the number and percentage of participants with AEs leading to discontinuation of Lokelma will be presented by SOC and PT, and the number and percentage of participants with any AE will be presented by SOC, PT, and relationship to Lokelma as assessed by the investigator. Each of these summaries will also include the number of events.

All AEs, SAEs, AEs that led to withdrawal or death and treatment-related AEs will be included in per-patient listings.

Clinical safety laboratory assessments will be summarised and listed. Shift tables will be provided for select tests, where shift from screening baseline to the worst value within each of study periods will be summarised. Laboratory data outside the reference ranges will be indicated in all listings.

All safety analyses will be performed on the Safety Set. In general, safety assessments will be reported descriptively by treatment group and/or study period. Full details on safety analyses will be provided in the SAP.

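### Safety objective #2 asks about electrolyte levels as well as incidence, but only below-cut-off counts are compared between the baths, and the cut-offs contradict each other

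*Protocol*

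**What the plan says.** **Objective.** In the synopsis and Section 2.3, safety objective #2 carries the heading "Incidence of Dialysis-related Hypokalemia, Hypomagnesemia, Hypophosphatemia, or Low Calcium". The sentence beneath it asks for something else: the levels of potassium, magnesium, calcium and phosphate "during dialysis (measured promptly prior to the termination of dialysis) during experimental treatment [2] compared to standard treatment [3"]. A note makes each electrolyte its own objective.

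**Outcome measure.** The measure is the number of values below a threshold. Section 8.4.7 states the rule: "All episodes where a specific electrolyte falls below the above listed threshold will be considered an" event for that electrolyte. Section 8.5.6 repeats it and says the totals are recorded over both phases, ending with the "8-week Treatment Phase-2 cross-over periods and compared between the treatments".

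**Data.** The notes to Table 1 schedule the end-of-dialysis Piccolo sample "within 30 minutes prior to rinse back on Mondays or Tuesdays after each long dialysis weekend (i.e., weekly"). Magnesium is drawn on the same weekly schedule and measured at the local laboratory. Each completer is therefore due 8 values per electrolyte on each bath.

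**Levels.** Section 8.5.1 plans by-visit descriptive statistics for quantitative safety parameters. Section 8.5.6 plans laboratory summaries, listings and shift tables for select tests, adds that "In general, safety assessments will be reported descriptively by treatment group and/or study period", and leaves full detail to the SAP.

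**Cut-offs.** For potassium, Section 2.3 counts events "where a Piccolo POCT measurement of K + is < 3.5 mEq/L", as does the synopsis; Sections 8.4.7 and 8.5.6 use below 2.0 mEq/L. For calcium, the synopsis and Sections 2.3, 8.4.7 and 8.5.6 use below 7.0 mEq/L. Section 5.2.1 points back to Section 2.3 but uses below 2.5 mEq/L, for pre- or post-dialysis values.

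**The concern.** A count of values below a cut-off does not estimate a difference in levels. Two baths can leave patients at different end-of-dialysis levels and still give similar counts, if both distributions lie mostly on one side of the cut-off.

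No other endpoint in the protocol fills the gap. Safety endpoint #1 is a count. Secondary endpoint #2 scores potassium as inside or outside a range. The exploratory objective relates levels to clinical events, not to the bath.

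This matters because the rationale in Section 1.2 is that low potassium during dialysis drives arrhythmia and that a 3.0 K bath reduces it. The end-of-dialysis level is the direct check on that mechanism. For the other three electrolytes, the dialysate change is in potassium only (calcium is 2.5 in both baths), so any shift may well be modest. Small shifts are where counting loses most.

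**Working it through.** **The plan's own figure.** There is none for this objective. The only power statement (Section 8.2, over 90% with 40 per sequence) concerns atrial fibrillation events. From it I take only 2 × 40 = 80 completers.

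**Information kept by a count.** For a normal variable with a share p of values below cut-off c (in SD units), the efficiency of the below-cut-off indicator relative to the mean, for a small shift, is

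E = φ(c)² / [p(1 − p)].

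- p = 0.50: 0.3989² / 0.25 = 0.64
- p = 0.10: 0.1755² / 0.09 = 0.34
- p = 0.01: 0.02665² / 0.0099 = 0.07

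**In terms of power.** Suppose a comparison of levels had 80% power at two-sided 5%. The count would have Φ[√E × (1.960 + 0.842) − 1.960]. At p = 0.50 this is Φ(0.798 × 2.802 − 1.960) = Φ(0.275) = 61%. The other values follow in the same way.

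| Share below cut-off | Relative efficiency | Power of count when levels have 80% |
|---|---|---|
| 50% | 0.64 | 61% |
| 20% | 0.49 | 50% |
| 10% | 0.34 | 37% |
| 5% | 0.22 | 26% |
| 1% | 0.07 | 11% |

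**Check in the crossover layout.** All inputs except the 80 completers and 8 weekly values are assumed: total SD 1, within-patient correlation 0.5, paired t-tests on patient means and on patient counts. For a 0.15 SD shift with no patient-by-period variation, the standard error for levels is √(2 × 0.5 / 8 / 80) = 0.0395. Then z = 0.15 / 0.0395 = 3.8, and power is about 97% by the normal approximation, against 96% simulated.

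| Shift; patient-by-period SD | Levels | Count, 50% below | 25% | 10% | 2% |
|---|---|---|---|---|---|
| 0.15 SD; 0 | 96% | 73% | 63% | 39% | 13% |
| 0.15 SD; 0.3 | 70% | 48% | 42% | 26% | 10% |
| 0.20 SD; 0.3 | 92% | 75% | 65% | 43% | 15% |

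At shifts of 0.3 SD or more with a central cut-off, both methods are near 100% and the difference disappears.

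**What the potassium contradiction does.** Assume an end-of-dialysis mean of 3.2 to 3.8 and an SD of 0.4 to 0.6 mEq/L.

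- Below 3.5: from Φ[(3.5 − 3.8)/0.4] = Φ(−0.75) = 23% to Φ[(3.5 − 3.2)/0.4] = Φ(0.75) = 77%. This is a fairly central cut-off.
- Below 2.0: at most Φ[(2.0 − 3.2)/0.6] = Φ(−2) = 2.3%, and practically zero at the other end. Of 80 × 8 = 640 values per bath, that is 0 to about 15.

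The same endpoint is therefore informative under one stated cut-off and nearly empty under the other.

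**The case against.** There are four fair points in favour of the plan.

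- **The heading, outcome measure, endpoint definition and analysis text all say incidence.** Only one sentence says levels. This stands: a reader might infer that the planned analysis fails to answer the objective, but counts answer the incidence question directly. For a safety objective about low values they are also the measure closest to the stated harm, so nothing here supports demoting them.
- **Levels are not discarded.** This also stands, given the descriptive summaries in Sections 8.5.1 and 8.5.6. Section 8.5.1 further promises 95% intervals with all point estimates. However, no between-bath difference in level is named as an estimate, so that promise does not supply one, and by-visit means are not a within-patient contrast.
- **No test, alpha or power is set for this objective, and safety is in general descriptive.** This stands. A reader might take the power figures as a shortfall against a planned test. They are not; they only illustrate how much information each summary carries.
- **Detail is left to the SAP, which may add a model for levels.** This stands in part. A missing model specification would be no finding. But the protocol itself fixes the endpoint as counts and names counts as what is compared, and the mismatch with its own objective sentence sits in the protocol.

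**Conclusion.** The point holds as a mismatch within the protocol. The objective's sentence asks for levels on experimental against standard treatment; the only stated treatment comparison concerns counts; and the levels part has no stated contrast.

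The 64%, 34% and 7% figures rest on normality and on the assumed share of values below the cut-off. The protocol gives no SDs, expected shifts or event shares, so the loss in this trial cannot be stated. A reader might infer a material loss for every electrolyte, and the documents do not support that. Potassium is the electrolyte deliberately changed, and a large shift with a cut-off near the middle of the values would leave little or no loss.

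The contradictory cut-offs need no assumption. Potassium below 3.5 against below 2.0 mEq/L, and calcium below 7.0 against below 2.5 mEq/L, cannot both define the same events. A comparison of levels does not depend on how they are settled; the counts depend on it entirely.

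This is an inexpensive improvement to a safety objective and does not touch the primary analysis.

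**What to change.** In Sections 2.3, 8.4.7 and 8.5.6, and in the synopsis to match:

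1. Keep the below-threshold counts as the incidence measure.
2. Add, separately for each electrolyte, the 3.0 K minus 2.0 K mean difference in scheduled weekly end-of-dialysis level with its 95% CI. Estimate it from a repeated-measures crossover model with treatment, period and sequence as fixed effects and patient and patient-by-period as random effects.
3. Reconcile the potassium cut-off between the synopsis and Section 2.3 on one side and Sections 8.4.7 and 8.5.6 on the other. Reconcile the calcium cut-off, and the sampling time it applies to, between Section 5.2.1 and the other sections. Which values are intended is for the sponsor to settle.

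The cost is wording in the protocol and SAP, four simple models on data already scheduled, and one more estimate per electrolyte to report. No new samples or patients are needed. If the sponsor intends incidence alone, the minimum change is to reword the objective's sentence to say so and to make the cut-offs agree.
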